APPENDIX A
Additional Details Pertaining to Study Design for Clinical Trials

Appendix A must be completed for investigator/student initiated research projects that require review by the convened board. For example, studies that use investigational test articles, that present more than minimal risk to subjects, or that involve prisoners, must be reviewed by the convened board.

Note that for studies requiring review by the convened board the full board application must be completed, data safety monitoring must be addressed (e.g. by completion of Appendix B to the main application) and the Investigator Brochure and /or package insert must also be submitted if available.

1. *For a clinical trial (e.g. a Phase I, II or III study), the use of the intervention must be fully described e.g., the treatment regimen for use of drugs, placebo, medical device etc. Also include plans for receipt of test article, storage, dispensing and reconciliation.:*

Treatment Regimen: We will administer a 6-week course of therapy, consistent with instruction on the package insert. Subjects will receive nicotine or placebo inhaler (1:1 ratio). Pfizer Pharmaceuticals has agreed to supply us with nicotine inhaler and placebo treatments (see letter of support). To enhance compliance and to confirm patient reports and proper inhaler use, subjects will be asked to keep a daily diary of the number of cartridges used and to return all cartridges at the next study visit. Subjects will be instructed to return study medication when they receive their reminder telephone call regarding upcoming appointments. For convenience, subjects will receive a plastic container to transport study drug. Patients will be instructed on an individualized basis to taper their use over the next 6 weeks. If a study subject does not quit smoking during the first 6 weeks of active treatment, it is unlikely that she will quit during the medication taper. Consequently, at visit 5 (6 week visit), subjects who have not quit smoking (7 day point prevalence abstinence confirmed with exhaled carbon monoxide measurement) will be discontinued from medication treatment and reminded to return all study medication.

Subjects will be instructed to begin using the inhaler on their quit date. Our choice of dosage is aimed at relieving withdrawal symptoms, so we will encourage heavier smokers to use more inhaler cartridges than lighter smokers. Subjects who smoke ≥ 10 CPD will be instructed to begin with 4-12 cartridge inhalers/day, which is consistent with other inhaler studies that have recommended a minimum use of 2 inhalers per day [67], or 4 inhalers per day [66], although use of at least 6 inhalers per day was recommended by others [40], including the package insert. However, clinical efficacy is observed with use of at least 4 cartridges per day, which is the minimum dose we will recommend for women who smoke ≥ 10 CPD. Women who smoke 5-9 CPD will be instructed to begin by using 1-4 cartridge inhalers/day, based on an estimated 1-2 mg of nicotine per cigarette, with each cartridge inhaler estimated to release 4 mg of nicotine [6]. Use of 1-4 cartridges/day by 4 light smokers in the pilot study resulted in 62% nicotine replacement. Dosage adjustments will be made in response to withdrawal symptoms and cotinine levels. We will monitor cotinine levels after the women have used the inhaler for 2 weeks. Subjects will be notified by the research nurse if there is a significant increase in cotinine above baseline values while smoking (see DSMP for cotinine monitoring). In our previous study [1], this approach worked well previously to ensure that cotinine levels were not excessive.

Receipt: We will have study personnel (the same person who will dispense the medication) transport study medication from UCONN to Baystate or Hartford Hospital and place it in the locked cabinet. If for some reason the study nurse is unable to transport drug, a research staff will pick up the drug from pharmacy and transport to Baystate to give to study nurse who will sign off that she received the medication. A signature log has been developed for drug transport and receipt (see drug accountability log).

Nicotine Replacement for Smoking Cessation during Pregnancy

Storage: Drug will be stored on site in locked filing cabinet. A temperature log, which can be downloaded on a weekly basis, will provide evidence that the medication is kept within recommended guidelines (not to exceed 77 degrees Fahrenheit).

Dispensing and reconciliation: The study medication will be dispensed by the research nurse at baseline, Visit 2, and Visit 4 . At or before the baseline visit, the study nurse will fax key variables for a given subject to the research pharmacist at UCONN who will enter these variables into a specially developed computer algorithm. Once the pharmacist enters these variables into the computer program, the computer assigns a treatment assignment. The pharmacist will communicate with the study nurse (by fax or e-mail) which medication box # to dispense to the subject. Boxes of nicotine and placebo inhaler will be labeled with a study number, kept at study sites in a locked filing cabinet (with a daily temperature log) in a research room or research pharmacy depending on the site.

Reconciliation: At every visit, subjects are asked to return used cartridges and unused medication. Used cartridges will be validated with patient reports of study records of use. Unused medication will be sent back to pharmacy where it will be destroyed.

2. *Provide a description of known adverse events due to the intervention and the plan to deal with such adverse events (e.g. does reduction, removal of device, removal from trial.):*

A. Potential Risks:

The potential risks for subjects include blood drawing, psychological tests, breach of confidentiality, and risk of medication (adverse effects and serious adverse events and increased nicotine exposure). Medical histories will be reviewed prior to entry into the study at screening and subjects will be under medical supervision while in the study. Trained phlebotomists will draw all blood samples. Blood drawing may result in slight discomfort, bruising, or there may be soreness at the puncture site. In some instances, dizziness or fainting may occur.

It is not known which of the adverse pregnancy outcomes associated with cigarette smoking may be a result of nicotine. These adverse effects include 1) spontaneous abortion; 2) preterm delivery; 3) low birth weight; 4) preterm delivery or preterm premature rupture of membranes; 5) placenta abruption and placenta previa; 6) sudden infant death syndrome.

In phase 3 studies, the most common side effects with nicotine inhaler include cough, throat irritation, rhinitis and mouth irritation. We expect that these side effects will also occur in our population.

The physiological, subjective and behavioral measures of withdrawal, will be physically noninvasive and should present no psychological and minimal medical risk to the subject.

Although uncomfortable, withdrawal symptoms do not pose significant health risks smoking cessation results in increased irritability, anxiety, tension, depression, increased hunger and drowsiness. Some individuals may be a risk for depression with smoking cessation. This is particularly true for persons with a past history of depression.

B. Procedures to minimize risks:

- 1) **Blood draw-** sterile techniques will be utilized for blood drawing to reduce the risk of infection.
- 2) **Risk of breach of confidentiality-** All data obtained through questionnaires will be kept in a double lock system. Data collected at study visits will take the form of subjective measures (case report forms) and/or directly into the REDCap system. REDCap (Research Electronic Data Capture) is a secure, web-based application designed to support data capture for research studies, providing: 1) an intuitive interface for validated data entry; 2) audit trails for tracking data manipulation and export procedures; 3) automated export procedures for seamless data

Nicotine Replacement for Smoking Cessation during Pregnancy

downloads to common statistical packages; and 4) procedures for importing data from external sources. An electronic file that links patient name and number will be maintained and managed using REDCap electronic data capture tools hosted at UConn Health.

Once a subject has completed the study the informed consent form and the case report form with identifiable information (subject information/locator information) will be kept at the site of recruitment in a locked file cabinet. The rest of the case report forms that do not contain identifiable data will be sent to UConn Health. Once the study is closed in the IRB, all data will be sent to IRON mountain for long term storage until the data can be destroyed per IRB and FDA regulations.

- 3) **Psychological testing-** trained personnel will administer psychological tests.
- 4) **Medication adverse events:** a) inhaler adverse effects---To minimize potential adverse effects of the inhaler we will a) instruct subjects on proper usage; b) inform subjects to stop medication use 6 weeks after the quit date if they have not completely quit smoking. c) procedure to minimize the risk of increased nicotine exposure--- Although cotinine concentrations are not typically measured during smoking cessation trials, pregnant women are considered a vulnerable population who may be at risk for adverse effects from nicotine. Therefore we would like to ensure that subjects do not receive increased overall nicotine exposure from the nicotine inhaler than is usually obtained from smoking. As stated in the consent we recommend that subjects quit smoking completely when they start inhaler use. Serum cotinine concentrations will be collected at baseline (i.e., while smoking), and at visit 2 (approximately 1-2 weeks after inhaler use). After sample collection of serum from baseline and visit 2, these samples will be sent out for analyses to Yale University where samples will be analyzed on a weekly basis (see attached letter of support). The R.N. responsible for ongoing patient care at each site will keep a log of cotinine concentrations for each subject while smoking and while on nicotine or placebo inhaler. Subjects will be notified immediately by the R.N. if their cotinine concentrations obtained at visit 2 exceeds concentrations obtained while smoking. A serum cotinine concentration while on treatment that exceeds a subject's baseline or screening smoking levels by 40% will be considered an increase in overall nicotine exposure. Please note that this is a conservative approach because the normal individual variation of serum cotinine in pregnant women who continue to smoke is 30% (Oncken, et al 1996). If a subject is notified to decrease her inhaler use accordingly (or completely quit smoking if she is not totally abstaining from cigarettes). A repeat cotinine concentration will be repeated within a week on the new dosage regimen. If the repeat cotinine is elevated compared to baseline values as described above, the medication will be stopped. It is also noteworthy that we are examining an intermittent nicotine delivery system in this study in an attempt to minimize nicotine exposure. It would be difficult for a subject to smoke and use the inhaler at the same time, so we anticipate that nicotine exposure will not exceed baseline levels while smoking. Also, if a subject clinically significantly increases her smoking while on treatment [ie., 1) she stopped smoking at visit 2 using the inhaler, but starts smoking at a later visit and continues to use the inhaler or 2) if she increases the average number of cigarettes per day over the previous 7 days by 25% compared to visit 2], we will perform a repeat cotinine test at the visit where this is identified. A significant change in smoking patterns and/or inhaler use will be decided by the research nurse. If this cotinine test is elevated compared to baseline levels, the elevated cotinine will be handled as above. Subject's who discontinue the study early will be asked to return the inhaler, including any unused cartridges, and no inhalers will be dispensed to the subject from this point.

If for any reason we are unable to obtain blood for serum cotinine, overall nicotine exposure will be assessed with the nicalert urine test at each visit. With this system there are 5 levels of exposure (Level 0: 1-10, Level 1: 10-30, Level 2: 30-100, Level 3: 100-200, Level 4: 200-500, Level 5: 500-1000, and Level 6 1000 plus) and an increase in any

Nicotine Replacement for Smoking Cessation during Pregnancy

level would be consistent with an increase in exposure. This type of monitoring was utilized in one clinical trial that was monitored by the FDA to estimate overall nicotine exposure in pregnant women (33).

- 5) **Pregnancy adverse problems**--We are only including subjects with chronic stable medical problems and no imminent pregnancy problems will be enrolled into the study. If there are any questions regarding current pregnancy problems the case will be discussed with the primary care provider (after obtaining consent from subject) and also reviewed with study obstetricians. We are monitoring nicotine exposure in both groups which may decrease the risk of adverse pregnancy problems. Additionally, women receive a comprehensive behavioral intervention designed to help them quit smoking, which should decrease the risk of pregnancy adverse effects. Women are monitored closely throughout the study and if an adverse event occurs consultation and treatment will be coordinated with their obstetrician.
- 6) **Withdrawal and worsening mood symptoms**-- although uncomfortable, nicotine withdrawal symptoms (irritability, craving for cigarettes, insomnia, increased appetite/weight gain, depressed mood) do not propose a significant medical risk. Nicotine replacement is designed to relieve withdrawal symptoms. Some studies suggest that especially persons with a history of depression may be at an added risk of depression with smoking cessation; however, we did not observe this in our last study (Oncken et al., 2008). If depressive symptoms occur (as evidenced by patient report or worsening symptoms on the beck questionnaire), the subject will be seen by a masters level counselor or [name]. [name] will help devise the treatment plan. Subjects who experience significant increases in depressed mood will be referred for further evaluation and treatment.

3. Describe circumstances that may lead to a subject being removed from the trial by the PI, e.g. due to failure to follow study procedures, and the process for doing so:

We do not foresee withdrawing any subject from the study (since it is important to have as much information as possible in an efficacy and safety study), but may withdraw study drug if a subject is noncompliant or has a serious adverse event, or if they are still smoking after 6 weeks of treatment. If a participant either withdraws from the study or the investigator decides to discontinue a participant due to SAE, the participant will have appropriate follow-up medical monitoring. Monitoring will continue until the problem requiring hospitalization was resolved or stabilized with no further change expected, is clearly unrelated to study medication, or results in death.

4. Describe any stopping rules for the study:

The stopping rules will be established at the first DSMB meeting, and agreed upon by both the investigative team and the DSMB. We propose to place particular emphasis was made on monitoring of overall serious adverse events, nicotine exposure, and efficacy rates. We propose that the board review serious adverse events by treatment group on an ongoing basis (approximately twice a year or more or less often depending on subject accrual). As in our previous study, a table will be provided to the board with treatment groups designated as "A" and "B" in order to maintain study medication assignment blinding. The 4 types of events are (1) perinatal mortality (includes stillbirths, miscarriage after 28 weeks gestation, infant death), (2) spontaneous abortion (i.e., miscarriage prior to 28 weeks gestation), and (3) low birth weight (LBW) and (4) preterm delivery and (5) any other serious adverse events. General stopping rules proposed include 1) A significantly higher rate of subjects have low birth rates or other serious adverse events in group "A" or "B"; 2) determination that the increased incidence is related to study medication; 3) the emergence of unexpected serious adverse experience of unexpected serious adverse experience not specified in the study; 4) the board may recommend to stop the study after review of efficacy data once half the subject have been recruited if it appears to be little chance that a difference in efficacy will be observed between the 2 groups.

Nicotine Replacement for Smoking Cessation during Pregnancy

As in our last study, these proposed monitoring rules were used as guidelines. Raw data, percentages, and statistics (if requested) were presented to the DSMB meetings. The DSMB has the ultimate decision as to whether the blind should be broken and the trial should remain open.

5. Additional Comments by PI:

None

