Study staff will also accept referrals from each of the practice locations noted above. In addition, potential participants may refer themselves to the study by contacting study staff directly or by leaving their contact information on the study voicemail. These individuals will be contacted to determine if they are interested in participating in the study. For the convenience of our subjects, those who receive their prenatal care at a Baystate practice location outside of Baystate Medical Center will be offered the option of receiving study visits at their prenatal care location. The Clinical RN Study Coordinator will travel to the practice location to conduct study visits. Study drug will be dispensed at these visits in the same manner as it is dispensed at Baystate Medical Center. Study drug will be signed out from Baystate Investigational Pharmacy prior to the study visit and will be transported by the study RN to the site. The study drug will remain in the RN's possession until it is dispensed to the subject per the protocol; drug dispensing will be documented in the subject's record as well as in the study drug accountability log per protocol.

Pregnant smokers will first be identified by clinic personnel and referred to our recruiter after expressing an interest in study participation. Study sites will also utilize direct mailings and Internet advertising for recruitment purposes. Study personnel at Baystate will review CIS to assess potential eligibility of women identified in the daily appointment report of all women scheduled for OB appointments at Wesson Women's Clinic, Baystate Maternal-Fetal Medicine, Baystate Midwifery and Women's Health, Baystate Wesson Women's Group, Baystate Mary Lane, and Baystate Wing. Women identified as potential participants will be approached to determine if they are interested in participating in the study.

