Subjects who are eligible and wish to participate will be asked to provide written informed consent before any other information is obtained. Potential subjects 16 and 17 years of age enrolled in CT will require parental consent. After the subject gives informed consent, basic inclusion/exclusion criteria will be assessed. If there are questions regarding the appropriateness of the subject's study participation, eligibility will be reviewed by the study nurse and physician prior to randomization. Given the young age of the population, a proportion will be adolescent, which is responsive to the NIH policy concerning pediatric populations.

Screening Procedures and who will perform them: A study recruiter will accept study referrals, and perform screening procedures. If the study recruiter not available to speak with a referred potential subject, the study nurse or physician may obtain consent and perform screening procedures.

Screening procedures will include consent signing, assessing inclusion/exclusion criteria, and other contact information. The following questionnaires/assessments will be obtained:

Nicotine Replacement for Smoking Cessation during Pregnancy

1. **Demographics:** Age, education, race/ethnicity, income, and type of insurance (public or private),
2. **Smoking history:** We will inquire about past and current smoking, including CPD currently and prior to pregnancy, intention to quit, partner smoking, motivation to quit and number of years of smoking [20, 71]. We will also evaluate prior use of medication to stop smoking and other drugs, including symptoms of other drug abuse or dependence. Smoking social networks will be assessed with items on the smoking status of partner and friends, the number of household smokers, perceived support for staying abstinent and the composition of the household (age and relationship to the subject) [72]. The Fagerstrom Test for Nicotine Dependence [70], a 6-item scale (internal consistency = 0.61), will be used to measure dependence on nicotine.
3. **Screening medical and obstetrics history** will include the number of pregnancies, previous pregnancy outcomes (preterm, term, living, abortions), and information on any current pregnancy problems or underlying medical disorders (e.g., diabetes or HIV infection). Current and past drug abuse history will be recorded. Ongoing medications will be recorded.
4. **Vital signs** (blood pressure, pulse) and **weight** will also be recorded.

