5. **PHQ:** We have chosen to identify major psychopathology using the PRIME-MD Patient Health Questionnaire [74]. This questionnaire consists of nine questions that screen for depression. Each item yields a score of 0-3, and the highest possible total score for all items is 27. The scale can be used longitudinally to identify trends in depressed mood. Subjects with evidence of suicidal ideation or any other severe, acute psychiatric symptom (e.g., psychosis) will be excluded from the study. Subjects who answer “more than half the days” to 5 or more items will be excluded from the study. Since the questionnaire relies on patient self-report, all responses will be verified by the principal investigator, if a subject answers “more than half the days” to 5 or more items to confirm exclusion is warranted.
6. **Self-efficacy questionnaires:** Evaluates confidence to resist smoking across a number of different situations [60]. The scale yields a total score, as well as subscores for positive & negative affect situations, and habit/craving items. This scale has been a strong predictor of smoking outcomes in previous studies [73].
7. **Exhaled carbon monoxide measurement.** Subjects will be asked to blow into a machine that measures CO in parts per million (ppm). Levels <9 ppm are consistent with cigarette abstinence [69].
8. **Urine sample:** A urine sample will only be collected at BL, V2, V5, and V6 and analyzed only if serum can not be obtained. Urine will be tested using the NicAlert method.

The screening visit is expected to take 1.5 hours. The participant will be given a handout to record cigarette intake prior to subsequent study visits.

Study Procedures and who will perform them:

Baseline: Eligible subjects scheduled to return for a baseline (i.e. randomization) visit approximately 1 week after screening (+ 14 Days). The study nurse will review the patient's medical history and confirm current medical and pregnancy history. She will discuss each case with the study obstetrician (at the performance site) who will sign off on entry of subject into the study.

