Aim 3: In our completed study, the effect of nicotine gum appeared to depend on cigarettes per day during the pretreatment period. For light smokers, the cessation rates were 18% and 21% for the control and nicotine groups, respectively, while for heavy smokers the rates were 0% and 15%, respectively. Since a similar effect in a sample of 150 women would provide power=0.80, using a two-sided $\alpha=0.05$, our proposed sample of 360 pregnant smokers will provide more than adequate power to detect the effect.

Aim 4: is exploratory and no sample size was calculated.

Explain on what basis it is reasonable to assume that the sample size will be obtained:

Recruitment will take place over 39 months, requiring enrollment of approximately 9 subjects per month. In our previous study, we had an on-site recruiter at each site (Baystate and Hartford Hospital) and were able to screen 3 pregnant smokers and enroll 2 subjects/week (i.e.,1 subject/site). We will also recruit from CHS in Hartford, where we expect to recruit 1 subject/month. Recruitment sites will be provided with materials designed to raise awareness of the study, including posters and brochures to be displayed prominently in all clinic areas. We will also encourage referrals from clinicians in the surrounding areas at each site, and recruit through newspapers and maternity magazines. Based on our history of recruitment, we are confident that we can reach the proposed recruitment goal.

Subject characteristics:

- Age: **at least 16 years of age**
- Ethnicity: **Hispanic and non-Hispanic. All race and ethnic groups will be eligible**
- Gender: **F**
- Other characteristics - (e.g. primary language etc.): **English or Spanish speaking**

Inclusion Criteria:

- a) smoking at least 5 CPD for the preceding 7 days
- b) previous attempt to quit smoking during pregnancy by self report
- c) 13-26 weeks gestation
- d) at least 16 years of age
- e) able to speak English or Spanish;
- f) intent to carry pregnancy to term; and
- g) stable residence

Exclusion criteria:

Nicotine Replacement for Smoking Cessation during Pregnancy

- a) current drug or alcohol abuse or dependence (other than methadone maintenance)
- b) twins or other multiple gestation
- c) unstable psychiatric disorder
- d) unstable medical problems (e.g., pre-eclampsia, threatened abortion, hyperemesis gravidarum)
- e) known congenital abnormality.

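### Appendix A allows randomisation before the baseline visit, so women can be assigned before they attend, have their history re-checked or are signed off by the obstetrician

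*Combined protocol and SAP*

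**What the plan says.** Under Study Procedures, Baseline, the protocol states: "Eligible subjects scheduled to return for a baseline (i.e. randomization) visit approximately 1 week after screening (+ 14 Days". The same paragraph lists two checks ahead of the randomisation step. First, "The study nurse will review the patient's medical history and confirm current medical and pregnancy history". Second, "She will discuss each case with the study obstetrician (at the performance site) who will sign off on entry of subject into the study". Randomization assignment comes next, as item 1 of the baseline list. The urn balances on three variables: history of preterm delivery, gestational age (below 19 weeks or not) and cigarettes per day (below 10 or not).

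Appendix A, item 1, Dispensing and reconciliation, gives a wider window: "At or before the baseline visit, the study nurse will fax key variables for a given subject to the research pharmacist at UCONN". It continues: "Once the pharmacist enters these variables into the computer program, the computer assigns a treatment assignment". The pharmacist then tells the nurse by fax or e-mail which numbered box to hand over.

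The Recruitment section lets women at outlying Baystate practices have study visits there, and says of those visits: "Study drug will be signed out from Baystate Investigational Pharmacy prior to the study visit and will be transported by the study RN".

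Some checking happens earlier. The Recruitment section says: "After the subject gives informed consent, basic inclusion/exclusion criteria will be assessed". Review by nurse and physician before randomisation is required only where a woman's suitability is in question.

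**The concern.** The two accounts of when randomisation happens do not agree, and the looser one has consequences. Baseline falls about 1 week after screening with 14 days' allowance, so up to about 3 weeks later. The Missed Visits item says that no-shows are common in this population. A woman assigned ahead of the visit may not come, may have developed an excluded condition such as pre-eclampsia, or may not be signed off.

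Each such case is an avoidable post-randomisation loss. The analysis section has no rule for women who are randomised but never treated. If they are kept as smokers they dilute the treatment difference. If they are dropped, the analysed groups are no longer those the urn balanced. Two of the three urn variables, gestational age and cigarettes per day, can also change between screening and baseline. The cigarettes-per-day cut matters further because Hypothesis 3 uses the same threshold.

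**Working it through.** **The order of events**

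1. Baseline text: the woman attends, history is confirmed, the obstetrician signs off, and assignment is the next listed step.
2. Appendix A: the fax may go at the visit or earlier, the pharmacist enters the variables, and the computer assigns. Attendance, re-check and sign-off are not named as conditions.
3. No other section holds the fax or the assignment until those steps are done. Followed literally, Appendix A therefore permits an order that the Baseline text does not.
4. Outlying Baystate practices: drug leaves the pharmacy before the visit, and the box to dispense is known only after assignment. If the nurse signs out only the assigned box, randomisation must come first. If she carries several coded boxes and receives the number on site, it need not. The text does not say which.

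**What a never-attending woman would lack**

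The Timeline of Study Procedures marks carbon monoxide and the Nicotine Use Survey at Screen, and smoking history taken at screening includes cigarettes per day. Cotinine, biomarkers and the withdrawal scale first appear at Baseline, as does dispensing. So screening CO and cigarettes per day would exist, but there would be no baseline cotinine, biomarker or withdrawal values and no inhaler.

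**Stratum drift**

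The longest gap is about 7 + 14 = 21 days, or 3 weeks. A woman screened between 16 weeks (19 − 3) and just under 19 weeks could cross the 19-week cut before a late baseline. Cigarettes per day could cross 10 in either direction.

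**Size, as an illustration**

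Inputs from Sample size and justification, Aim 1: p1 = 0.149, p2 = 0.269, n = 180 per arm, two-sided alpha 0.05, stated power 0.80.

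Formula: power = Φ{[(p2 − p1) − 1.96·√(2·p̄(1 − p̄)/n)] / √([p1(1 − p1) + p2(1 − p2)]/n)}, where p̄ is the mean of p1 and p2.

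Plan's own figure: p̄ = 0.209, null standard error 0.0429, alternative standard error 0.0424. Then (0.120 − 1.96 × 0.0429)/0.0424 ≈ 0.85, giving power 0.802. The stated 0.80 reproduces.

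Now let a share f of all randomised women never attend, equally in both arms. If they count as smokers, both rates are multiplied by (1 − f) with n = 180. If they are dropped, the rates stay and n becomes 180(1 − f).

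| Assumed f | Women of 360 | Rates if counted as smokers | Power, counted as smokers | Power, dropped |
|---|---|---|---|---|
| 0 | 0 | 0.149 vs 0.269 | 0.802 | 0.802 |
| 2% | about 7 | 0.146 vs 0.264 | 0.792 | 0.794 |
| 5% | 18 | 0.142 vs 0.256 | 0.776 | 0.782 |
| 10% | 36 | 0.134 vs 0.242 | 0.748 | 0.759 |

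The values of f, the equal split between arms and both handling rules are assumptions. The inconsistency in timing depends on none of them.

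**The case against.** The strongest reply is that this is one loose phrase in an appendix. Women are consented and checked against the basic criteria at screening, doubtful cases are reviewed before randomisation, and nothing stops the obstetrician signing off early. *Before* may mean the previous day. Allocation is concealed and double-blind, so non-attendance before treatment should not differ by arm. An assigned box is not exposure, because the nurse keeps the drug until it is dispensed. The design section also speaks of 360 women receiving an inhaler, so those never treated might not count towards 360.

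Most of this stands, and it limits the harm to lost precision, incomplete data and weaker balance. It does not show bias between arms. It does not remove the conflict, since no section says what must be complete before the fax is sent.

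Three stronger readings are tempting and are not supported:

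- A reader might infer that the satellite sign-out rule forces early randomisation. It does not, because carrying several coded boxes is not excluded. The rule also covers later dispensing visits, when the woman is already assigned.
- A reader might infer that women are randomised with no eligibility check. What can be bypassed is the baseline re-check and, if left until then, the sign-off.
- A reader might take the earlier trial's experience ("were able to screen 3 pregnant smokers and enroll 2 subjects/week") to mean that up to a third could be lost after randomisation. That gap includes women found ineligible at screening, who would not be booked for baseline, so it gives no usable bound.

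**Conclusion.** The point holds as an inconsistency with a practical consequence. Appendix A allows assignment before the baseline visit, while the Baseline section puts randomisation, history re-check and sign-off at that visit. For outlying Baystate practices, the sign-out rule may in practice require early assignment.

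The likely cost is modest. At assumed non-attendance of 2% to 10% across the whole trial, power would be about 0.79 to 0.75 with such women counted as smokers, against 0.80 planned. The documents give no rate. If early assignment happened only at the outlying practices, the trial-wide share would be smaller than the non-attendance rate there. This is a cheap improvement that prevents avoidable losses. It is not a threat to the validity of the comparison.

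**What to change.** - In Appendix A, Dispensing and reconciliation, delete the words *or before*.
- There and in Randomization assignment under Baseline, state that the urn variables are sent only after the woman has attended, her gestational age, cigarettes per day and eligibility have been re-confirmed, and the obstetrician's sign-off is recorded.
- Reconcile the Recruitment section with this, so that at satellite baseline visits the box number is obtained during the visit, for example from several coded boxes carried by the nurse.
- It would also help to state how a woman who is randomised but never treated is analysed, and whether she counts towards 360.

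The cost is protocol wording, a short wait for the pharmacist's reply at the baseline visit, and a few extra boxes to log and return.
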